#### **7.2.3.2 Events of Clinical Interest**

Selected non-serious and serious adverse events are also known as Events of Clinical Interest (ECI) and must be reported within 24 hours to the UCLA DSMB and within 2 working days to Merck Global Safety. (Attn: Worldwide Product Safety; [contact]).

For the time period beginning when the consent form is signed until treatment allocation/randomization, any ECI, or follow up to an EVI, that occurs to any subject must be reported within 24 hours to the Sponsor and within 2 working days to Merck Global Safety if it causes the subject to be excluded from the trial, or is the result of a protocol-specified intervention, including but not limited to washout or discontinuation of usual therapy, diet, placebo treatment or a procedure.

For the time period beginning at treatment allocation/randomization through 90 days following cessation of treatment, or 30 days following cessation of treatment if the subject initiates new anticancer therapy, whichever is earlier, any ECI, or follow up to an ECI, whether or not related to Merck product, must be reported within 24 hours to the Sponsor and within 24 hours to Merck Global Safety.

. Events of clinical interest for this trial include:

1. An overdose of Merck product, as defined in Section 7.2.1 - Definition of an Overdose for This Protocol and Reporting of Overdose, that is not associated with clinical symptoms or abnormal laboratory results.
2. An elevated AST or ALT lab value that is greater than or equal to 3X the upper limit of normal and an elevated total bilirubin lab value that is greater than or equal to 2X the upper limit of normal and, at the same time, an alkaline phosphatase lab value that is less than 2X the upper limit of normal, as determined by way of protocol-specified laboratory testing or unscheduled laboratory testing.\*

\*Note: These criteria are based upon available regulatory guidance documents. The purpose of the criteria is to specify a threshold of abnormal hepatic tests that may require an additional evaluation for an underlying etiology

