### **5.1.3 Subject Exclusion Criteria**

The subject must be excluded from participating in the trial if the subject:

1. Has received prior therapy with an EGFR tyrosine kinase inhibitor (such as erlotinib, gefitinib, afatinib, rociletinib, or AZD9291) for NSCLC.
2. Is currently participating or has participated in a study of an investigational agent or using an investigational device within 30 days of the first dose of trial treatment. The 30 day window should be applied to the last dose of an antineoplastic investigational agent or last use of an investigational device with antineoplastic intent.
3. Is receiving systemic steroid therapy within three days prior to the first dose of trial treatment or receiving any other form of immunosuppressive medication (corticosteroid use on study for management of ECIs is allowed).
4. Is expected to require any other form of systemic or localized antineoplastic therapy while on trial (including maintenance therapy with another agent for NSCLC or radiation therapy).
5. Has received prior systemic cytotoxic chemotherapy, antineoplastic biological therapy (e.g., cetuximab), major surgery within 3 weeks of the first dose of trial treatment; received thoracic radiation therapy of > 30 Gy within 6 months of the first dose of trial treatment.
6. Has received prior therapy with an anti-PD-1, anti-PD-L1, anti-PD-L2, anti-CD137, or anti-Cytotoxic T-lymphocyte-associated antigen-4 (CTLA-4) antibody (including ipilimumab or any other antibody or drug specifically targeting T-cell co-stimulation or checkpoint pathways). Has participated in another pembrolizumab clinical trial.

7. Has a known history of prior malignancy that in the opinion of the investigator interferes with the ability to interpret the radiographic results (e.g. a second active malignancy with some lesions being of uncertain origin).
8. Subjects with central nervous system (CNS) metastases and/or carcinomatous meningitis may participate provided they are clinically stable, and are using no steroids for at least seven days prior to study medication.

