#### 5.2.1.2 Dose Modification

Adverse events (both non-serious and serious) associated with pembrolizumab exposure may represent an immunologic etiology. These adverse events may occur shortly after the first dose or several months after the last dose of treatment. Pembrolizumab must be withheld for drug-related toxicities and severe or life-threatening AEs as per Table 3 below. See Section 5.6.1 for supportive care guidelines, including use of corticosteroids.

Table 3

Dose Modification Guidelines for Drug-Related Adverse Events

General instructions:

 
1. Corticosteroid taper should be initiated upon AE improving to Grade 1 or less and continue to taper over at least 4 weeks.
 
2. For situations where pembrolizumab has been withheld, pembrolizumab can be resumed after AE has been reduced to Grade 1 or 0 and corticosteroid has been tapered. Pembrolizumab should be permanently discontinued if AE does not resolve within 12 weeks of last dose or corticosteroids cannot be reduced to <math>\leq 10</math> mg prednisone or equivalent per day within 12 weeks.
 
3. For severe and life-threatening irAEs, IV corticosteroid should be initiated first followed by oral steroid. Other immunosuppressive treatment should be initiated if irAEs cannot be controlled by corticosteroids.
 

Immune-related AEs	Toxicity grade or conditions (CTCAEv4.0)	Action taken to pembrolizumab	irAE management with corticosteroid and/or other therapies	Monitor and follow-up
Pneumonitis	Grade 2	Withhold	
 
Administer corticosteroids (initial dose of 1-2 mg/kg prednisone or equivalent) followed by taper
 
	
 
Monitor participants for signs and symptoms of pneumonitis
 
Evaluate participants with suspected pneumonitis with radiographic imaging and initiate corticosteroid treatment
 
Add prophylactic antibiotics for opportunistic infections
 

	Grade 3 or 4, or recurrent Grade 2	Permanently discontinue		

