## **5.3 Concomitant Medications/Vaccinations (allowed & prohibited)**

Medications or vaccinations specifically prohibited in the exclusion criteria are not allowed during the ongoing trial. If there is a clinical indication for one of these or other medications or vaccinations specifically prohibited during the trial, discontinuation from trial therapy or vaccination may be required. The investigator should discuss any questions regarding this with the Merck Clinical team. The final decision on any supportive therapy or vaccination rests with the investigator and/or the subject's primary physician.

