### **5.3.2 Prohibited Concomitant Medications**

Subjects are prohibited from receiving the following therapies during the Screening and Treatment Phase (including retreatment for post-complete response relapse) of this trial:

- Antineoplastic systemic chemotherapy or biological therapy
- Immunotherapy not specified in this protocol
- Chemotherapy not specified in this protocol
- Investigational agents other than pembrolizumab
- Radiation therapy

- Note: Radiation therapy to a symptomatic solitary lesion or to the brain may be allowed at the investigator's discretion.
- Live vaccines within 30 days prior to the first dose of trial treatment and while participating in the trial. Examples of live vaccines include, but are not limited to, the following: measles, mumps, rubella, varicella/zoster, yellow fever, rabies, BCG, and typhoid vaccine.
- Systemic glucocorticoids for any purpose other than to modulate symptoms from an event of clinical interest of suspected immunologic etiology. The use of physiologic doses of corticosteroids may be approved.

Subjects who, in the assessment by the investigator, require the use of any of the aforementioned treatments for clinical management should be removed from the trial. Subjects may receive other medications that the investigator deems to be medically necessary.

The Exclusion Criteria describes other medications which are prohibited in this trial.

There are no prohibited therapies during the Post-Treatment Follow-up Phase.

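### The ECI list in 7.2.3.2 omits the immune-related events that other sections call ECIs, and the sections disagree on recording non-serious immune events after day 30

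*Combined protocol and SAP*

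**What the plan says.** **The term.** Section 7.2.3.2 holds the protocol's only list of events of clinical interest (ECIs), introduced by "Events of clinical interest for this trial include". It has two entries. One is an overdose with no symptoms or abnormal laboratory results. The other is AST or ALT at least 3 times the upper limit of normal, with bilirubin at least 2 times and alkaline phosphatase below 2 times that limit. Section 5.3.1 relies on Section 7.2 for the definition.

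**Where it is used for immune events.** Exclusion 3 notes that "corticosteroid use on study for management of ECIs is allowed". Section 5.3.2 lists as prohibited during screening and treatment "Systemic glucocorticoids for any purpose other than to modulate symptoms from an event of clinical interest of suspected immunologic etiology", and says that subjects who "require the use of any of the aforementioned treatments for clinical management should be removed from the trial". The 5.4.1 note sends events judged unrelated to pembrolizumab to the ECI reporting guidance.

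**What Table 3 directs.** Table 3 (Section 5.2.1.2) directs corticosteroids for most immune-related events, and its general instructions add that "pembrolizumab can be resumed after AE has been reduced to Grade 1 or 0 and corticosteroid has been tapered".

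**Recording.** Section 7.2 records adverse events through 30 days after treatment. Section 5.6 also says 30 days, and 2.1 says at least 30 days. Section 7.1.2.1 has events graded and recorded during follow-up as well. Section 7.1.5.4 asks for an assessment of drug-related immune events at Follow-up Visit 1, 3 months after the last dose. After day 30, 5.3.1 records medications for SAEs and ECIs.

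**The concern.** Two rules depend on a term whose only list does not contain the events they are about. The first is the steroid exception in 5.3.2. Taken with the 7.2.3.2 list, it does not reach pneumonitis, colitis or the other non-hepatic immune events, although Table 3 tells the investigator to give steroids for them. The second is the reporting instruction in 5.4.1, which for those events points to no listed ECI.

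The recording conflict matters more. Section 5.2.1.2 warns that immune events can appear several months after the last dose, so late events are expected. The first secondary objective is safety by tabulating and grading adverse events. If the sections disagree on whether a late non-serious immune event goes on the case report form, that tabulation depends on which section the site followed.

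**Working it through.** No figure in the plan needs reproducing. The check sets the sections side by side.

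**Step 1: which Table 3 events fall outside the ECI list.** Table 3 has 10 immune-related rows: pneumonitis, diarrhea/colitis, liver tests, diabetes/hyperglycemia, hypophysitis, hyperthyroidism, hypothyroidism, nephritis, myocarditis, and all other.
- Three rows direct no corticosteroid in the table (diabetes/hyperglycemia, hyperthyroidism, hypothyroidism), so 10 − 3 = 7 do.
- One of the 7 is the liver row, which leaves 7 − 1 = 6 non-hepatic rows. None is on the 7.2.3.2 list.
- The liver row is covered only in part. Table 3 acts on raised AST/ALT or raised bilirubin, while the ECI needs both, with alkaline phosphatase below 2 times the limit.
- Section 5.4.1 also directs steroids for Grade 3–4 hyperthyroidism, which is not listed either.

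This count shows how much of the wording is affected. It is not a number of patients.

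**Step 2: what the two steroid rules imply for one event.** Take Grade 2 pneumonitis on treatment. Table 3 says withhold, give steroids, taper, then resume if the event has settled. The taper rule is "Corticosteroid taper should be initiated upon AE improving to Grade 1 or less and continue to taper over at least 4 weeks", which is longer than one 3-week cycle. Section 5.3.2, read with the 7.2.3.2 list, treats the same steroid as prohibited. The two rules cannot both be followed literally.

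**Step 3: recording windows for a non-serious immune event that is not a listed ECI.**
- Section 7.2: all adverse events, to 30 days after treatment.
- Section 5.6: 30 days. Section 2.1: a minimum of 30 days.
- Section 7.2.3.1: 90 days or new anti-cancer therapy, whichever is earlier, and at any time if related, but for serious events only.
- Section 7.2.3.2: 90 days, or 30 days if new therapy starts, but for ECIs only.
- Section 7.1.2.1: recorded during follow-up, with a reference to 7.2 for detail.
- Section 7.1.5.4: immune events assessed at 3 months, for patients who stopped for a reason other than progression.

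Three calendar months are 89 to 92 days. If treatment cessation and last dose are taken as the same date, the period in dispute up to Follow-up Visit 1 is 89 − 30 = 59 to 92 − 30 = 62 days, or about 60 days.

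**Step 4: what happens to one such event.** Suppose a patient stops without progression and has Grade 2 colitis on day 60, treated with oral steroids. Follow-up Visit 1 should detect it. Under 7.2 its recording window closed on day 30. Under 7.1.2.1 it is recorded. The steroid falls outside 5.3.1, because the event is neither serious nor a listed ECI, although 7.1.1.4.2 asks for medication taken during the trial. With about 25 patients, one event counted or omitted moves an incidence by 1/25 = 4 percentage points.

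**The case against.** On steroids, the case for leaving the text alone is strong. The exception in 5.3.2 speaks of suspected immunologic cause. The word introducing the ECI list can be read as open-ended. Table 3 and 5.4.1 give specific instructions event by event, and 5.6 does not name steroid use as a reason to discontinue. Section 5.3 adds that "The final decision on any supportive therapy or vaccination rests with the investigator" or the patient's primary physician, and 5.3.2 itself says that "There are no prohibited therapies during the Post-Treatment Follow-up Phase". A reader might infer that patients treated for immune toxicity would be removed from the trial. The documents do not support that: the permission is evident, and what remains is a definition that does not match its use.

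On recording, a layered reading is available: all events to 30 days, serious events and ECIs to 90 days, and drug-related immune events also at 3 months. The minimum in 2.1 is compatible with this, and 7.1.2.1 defers to 7.2. A reader might also take the reference in 7.2 to each examination as a competing, longer window, but it describes how events are entered and not for how long. These points narrow the conflict without closing it. Section 7.2, to which the others defer, has no third layer, and 5.3.1 does not extend to the steroids given for these events.

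A fair objection to a longer window is that toxicity from a subsequent EGFR TKI would confuse attribution. That stands, so the window needs a stop rule when new therapy starts.

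**Conclusion.** The point holds as a minor one. The ECI mismatch is a wording conflict between 5.1.3, 5.3.2, 5.4.1 and 7.2.3.2, with little likely effect on who stays on treatment. The recording conflict has the clearer consequence: for about 60 days, late non-serious immune events and their steroids may be assessed but not recorded, or recorded inconsistently.

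The effect is confined to the secondary safety objective. A reader might infer that serious toxicity would be missed or that the efficacy results are at risk. Neither follows: serious events keep their own window in 7.2.3.1, and response and survival follow-up do not depend on these sections.

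The 60-day figure assumes that last dose and treatment cessation coincide. The documents give no rate for late non-serious immune events, so no number of affected patients can be stated; the 4-point shift is the effect of a single event among about 25 patients.

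**What to change.** 1. In exclusion 3 and 5.3.2, replace the ECI exception with *immune-related adverse events managed under Table 3 or Section 5.4.1*, and state in 5.3.2 that such steroid use is not a reason for removal.
2. In 7.2, 5.6 and 5.3.1, record immune-related adverse events and their steroid treatment through Follow-up Visit 1, about 3 months after the last dose. If new anti-cancer therapy starts before then, record until the later of that start and 30 days after treatment. Align 2.1 and 7.1.2.1 with this. Section 7.1.5.4 gives Follow-up Visit 1 only to patients who stop without progression, so for the others use the existing visits or calls every 60 days in 2.1.
3. In the 5.4.1 note, refer to the adverse event and SAE reporting rules of Section 7.2.

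The cost is a protocol wording change and slightly more safety data entry. It needs no new visits or tests. Adding immune events to the ECI list for expedited reporting is not required and can be left to the sponsor.

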### **7.2.3.3 Protocol-Specific Exceptions to Serious Adverse Event Reporting**

Efficacy endpoints as outlined in this section will not be reported to Merck as described in Section 7.2.3.- Immediate Reporting of Adverse Events to the Sponsor and to Merck, unless there is evidence suggesting a causal relationship between the drug and the event. Any such event will be submitted to the Sponsor within 24 hours and to Merck Global Safety within 2 working days either by electronic or paper media.

Specifically, the suspected/actual events covered in this exception include any event that is disease progression of the cancer under study.

The Sponsor will monitor unblinded aggregated efficacy endpoint events and safety data to ensure the safety of the subjects in the trial. Any suspected endpoint which upon review is not progression of the cancer under study will be forwarded to Merck Global Safety as a SAE within 2 working days of determination that the event is not progression of the cancer under study

Hospitalization related to convenience (e.g.transportation issues etc.) will not be considered a SAE.

### **7.2.4 Evaluating Adverse Events**

An investigator who is a qualified physician will evaluate all adverse events according to the NCI Common Terminology for Adverse Events (CTCAE), version 4.0. Any adverse event which changes CTCAE grade over the course of a given episode will have each change of grade recorded on the adverse event case report forms/worksheets.

All adverse events regardless of CTCAE grade must also be evaluated for seriousness.

### **7.2.5 Sponsor Responsibility for Reporting Adverse Events**

All Adverse events will be reported to regulatory authorities, IRB/IECs, in accordance with all applicable global laws and regulations

Table 6 Evaluating Adverse Events

An investigator who is a qualified physician, will evaluate all adverse events as to:

V4.0 CTCAE Grading	Grade 1	Mild; asymptomatic or mild symptoms; clinical or diagnostic observations only; intervention not indicated.
	Grade 2	Moderate; minimal, local or noninvasive intervention indicated; limiting age-appropriate instrumental ADL.
	Grade 3	Severe or medically significant but not immediately life-threatening; hospitalization or prolongation of hospitalization indicated; disabling; limiting self-care ADL.
	Grade 4	Life threatening consequences; urgent intervention indicated.
	Grade 5	Death related to AE
Seriousness	A serious adverse event is any adverse event occurring at any dose or during any use of Merck product that:	
	† Results in death ; or	
	† Is life threatening ; or places the subject, in the view of the investigator, at immediate risk of death from the event as it occurred (Note: This does not include an adverse event that, had it occurred in a more severe form, might have caused death.); or	
	† Results in a persistent or significant disability/incapacity (substantial disruption of one’s ability to conduct normal life functions); or	
	† Results in or prolongs an existing inpatient hospitalization (hospitalization is defined as an inpatient admission, regardless of length of stay, even if the hospitalization is a precautionary measure for continued observation. (Note: Hospitalization for an elective procedure to treat a pre-existing condition that has not worsened is not a serious adverse event. A pre-existing condition is a clinical condition that is diagnosed prior to the use of a pembrolizumab and is documented in the patient’s medical history.); or	
	† Is a congenital anomaly/birth defect (in offspring of subject taking the product regardless of time to diagnosis); or	
Is a new cancer ; (that is not a condition of the study) (although not serious per ICH definitions, is reportable to the Sponsor within 24 hours and to Merck within 2 working days to meet certain local requirements.); or		

	
Is an overdose (whether accidental or intentional). Any adverse event associated with an overdose is considered a serious adverse event for collection purposes. An overdose that is not associated with an adverse event is considered a non-serious event of clinical interest and must be reported within 24 hours to the Sponsor and to Merck within 2 working days.
 
Other important medical events that may not result in death, not be life threatening, or not require hospitalization may be considered a serious adverse event when, based upon appropriate medical judgment, the event may jeopardize the subject and may require medical or surgical intervention to prevent one of the outcomes listed previously (designated above by a †).
	
Duration	Record the start and stop dates of the adverse event. If less than 1 day, indicate the appropriate length of time and units	
Action taken	Did the adverse event cause the Merck product to be discontinued?	
Relationship to Merck Product	
Did the Merck product cause the adverse event? The determination of the likelihood that the Merck product caused the adverse event will be provided by an investigator who is a qualified physician. The investigator's signed/dated initials on the source document or worksheet that supports the causality noted on the AE form, ensures that a medically qualified assessment of causality was done. This initialed document must be retained for the required regulatory time frame. The criteria below are intended as reference guidelines to assist the investigator in assessing the likelihood of a relationship between the test drug and the adverse event based upon the available information.
 
The following components are to be used to assess the relationship between the Merck product and the AE; the greater the correlation with the components and their respective elements (in number and/or intensity), the more likely the Merck product caused the adverse event (AE):
	
	Exposure	Is there evidence that the subject was actually exposed to the Merck product such as: reliable history, acceptable compliance assessment (pill count, diary, etc.), expected pharmacologic effect, or measurement of drug/metabolite in bodily specimen?
	Time Course	Did the AE follow in a reasonable temporal sequence from administration of the Merck product? Is the time of onset of the AE compatible with a drug-induced effect (applies to trials with investigational medicinal product)?
	Likely Cause	Is the AE not reasonably explained by another etiology such as underlying disease, other drug(s)/vaccine(s), or other host or environmental factors
Relationship to Merck Product	The following components are to be used to assess the relationship between the test drug and the AE: (continued)	
	Dechallenge	Was the Merck product discontinued or dose/exposure/frequency reduced? If yes, did the AE resolve or improve?

(continued)		
If yes, this is a positive dechallenge. If no, this is a negative dechallenge.          (Note: This criterion is not applicable if: (1) the AE resulted in death or permanent disability; (2) the AE resolved/improved despite continuation of the Merck product; or (3) the trial is a single-dose drug trial); or (4) Merck product(s) is/are only used one time.)

	Rechallenge	
Was the subject re-exposed to the Merck product in this study?          If yes, did the AE recur or worsen?          If yes, this is a positive rechallenge. If no, this is a negative rechallenge.          (Note: This criterion is not applicable if: (1) the initial AE resulted in death or permanent disability, or (2) the trial is a single-dose drug trial); or (3) Merck product(s) is/are used only one time).  NOTE: IF A RECHALLENGE IS PLANNED FOR AN ADVERSE EVENT WHICH WAS SERIOUS AND WHICH MAY HAVE BEEN CAUSED BY THE MERCK PRODUCT, OR IF REEXPOSURE TO THE MERCK PRODUCT POSES ADDITIONAL POTENTIAL SIGNIFICANT RISK TO THE SUBJECT, THEN THE RECHALLENGE MUST BE APPROVED IN ADVANCE BY THE U.S. CLINICAL MONITOR AS PER DOSE MODIFICATION GUIDELINES IN THE PROTOCOL.

	Consistency with Trial Treatment Profile	
Is the clinical/pathological presentation of the AE consistent with previous knowledge regarding the Merck product or drug class pharmacology or toxicology?

The assessment of relationship will be reported on the case report forms /worksheets by an investigator who is a qualified physician according to his/her best clinical judgment, including consideration of the above elements.
		
Record one of the following	
Use the following scale of criteria as guidance (not all criteria must be present to be indicative of a Merck product relationship).
	
Yes, there is a reasonable possibility of Merck product relationship.	
There is evidence of exposure to the Merck product. The temporal sequence of the AE onset relative to the administration of the Merck product is reasonable. The AE is more likely explained by the Merck product than by another cause.
	
No, there is not a reasonable possibility Merck product relationship	
Subject did not receive the Merck product OR temporal sequence of the AE onset relative to administration of the Merck product is not reasonable OR there is another obvious cause of the AE. (Also entered for a subject with overdose without an associated AE.)
	

